However the most of the literature on the use of changes in the ONSD for monitoring the changes in ICP came from the patients in the intensive care units with elevated intracranial pressure.^{2,7} Currently there are no data on how ONSD changes with acute increase or decrease in ICP. In addition, we don't know how soon the ONSD changes with acute changes in intracranial pressure.

Intracranial pressure is determined by the intracranial volume which in turn determined by the intracranial content namely, brain tissue, intracranial vessels (artery and veins) and the cerebrospinal fluid. There are limited non-surgical options that can be used to alter the ICP. Increase in the volume of intracranial vessels by either arterial dilation and/or occlusion of venous drainage can lead to increase in intracranial pressure. Carbon dioxide (CO₂) is a potent cerebral vasodilator, hypercapnia induced cerebral vasodilatation can lead to increase in ICP secondary to increase in intracranial volume. Similarly, obstruction to the cerebral venous drainage can also increase the intracranial pressure. Controlling the CO₂ and improving the venous drainage are the two fundamental principles in the anesthesia management of patients with increased ICP.^{6 8}

In order to use transorbital ultrasonographic measurement of ONSD as a method of monitoring changes in ICP, we need to determine how reliable the change in ONSD with controlled acute changes in intracranial pressure is. Controlled changes in ICP can be produced by either manipulation PCO₂ and/or cerebral venous

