All volunteers will be fully awake throughout the study and be kept comfortable. The transocular ultrasound examinations of the ONSD will be carried out using a SonoSite Edge (FUJI FILM SonoSite Inc. US) ultrasound system and a 7-10 MHz linear probe. Two trained investigators will perform investigations on both eyes of all subjects independently without being aware of each other's study results. All patients will be in the supine position and the probe will be gently placed on the temporal part of the closed upper eyelid. Contact with the eye will be gentle at all times and pressure never directly applied on the globe with the probe. A Tegaderm film (Transparent film dressing, 3M Canada) will be applied over the eye to protect the patient from the ultrasound gel applied during sonography. Once the anterior part of the optic nerve is depicted in the transverse/axial plane showing the papilla and optic nerve in its longitudinal course, the ONSD will be assessed 3 mm behind the papilla, as described previously (Figure 3). Each eye will be examined 3 times by each investigator and the mean value of the ONSD will be used for further calculations.

Carbon dioxide Manipulation

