The volunteers will don an airtight mask connected to the RespirAct™ sequential gas delivery breathing circuit. The subject will lie supine on a stretcher. Gas will be supplied by a computerized MPET system (RespirAct™). During control conditions, room air will be supplied at flows greater than the subject's minute ventilation. These studies will be done at the subject's baseline end-tidal CO₂ tension (usual range 35 – 40 mmHg). The PetO₂ will be fixed at 100 mmHg, a normal PETO₂ for most subjects. We will record baseline values for 120 seconds and then the PetCO₂ will be increased to +10 mmHg (Hypercapnia I) from baseline and held for 5 minutes in order to complete ONSD measurements. The venous compression neck collar will then be applied and ONSD measurements will be repeated. Following measurements, the PetCO₂ will be returned back to baseline (Figure 1). This sequence will again be repeated increasing the PetCO₂ to +15 mmHg (Hypercapnia II) from baseline before returning to baseline. The subject will then have PetCO₂ decreased to -10 mmHg (Hypocapnia) from baseline before returning to normal capnia. The study will stop at this point. During each cycle, the PetO₂ and PetCO₂ will be controlled by delivering mixes of source gases consisting of O₂, air, and blends of CO₂, N₂ and O₂. The speed and accuracy of the RespirAct™ for modulating PetCO₂ while maintaining constant PetO₂ is shown in Figure 2.

The RespirAct™ system has been used extensively in more than 15 UHN studies. Over 500 spontaneously breathing human subjects have been studied under these approved protocols. Results have been published in abstract and peer reviewed form and a number of Master's and Doctorate Theses at the University of Toronto ([name], [name], [name], [name], [name], [name], [name]). The RespirAct™ is still considered an

investigational device and Health Canada approval will be obtained before beginning the study.

Internal jugular compression using a Neck collar

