A custom made collar consisting of two (2 x 3 x 1.5 cm) soft gauze pledgets held over the IJV by an elastic retainer will be applied around the patient's neck which can be adjusted to the subject's neck circumference using Velcro.(Velcro, US) This will apply only minimal pressure on the neck, which is comparable to wearing a tight dress shirt. In order to confirm the jugular venous occlusion with the neck collar, we will measure the diameter and flow in the IJV using the ultrasound in each subject in both sitting and supine positions with and without collar. Similarly to determine the lowest pressure needed to occlude the IJV, a 100 ml fluid (normal saline) bag which is attached to a pressure manometer will be placed on the subjects' neck below the collar and the minimal pressure at which there is complete occlusion of IJV will be recorded. The venous compression neck collar will be applied at each CO₂ levels (normocapnia, Hypercapnia I and II and hypocapnia) and ONSD measurements will be measures before and after the collar.

Risks

1. Carbon dioxide

The physiologic stresses of CO₂ manipulation on this proposal can be considered minimal. The higher PetCO₂ required will not exceed 60 mmHg nor will this change be sustained for long (10 minute intervals). The lower level of PetCO₂ is frequently seen with exercise. This range of PetCO₂ is physiological and is experienced repeatedly by most people over a regular day. Hyperventilation with hypocapnic PetCO₂ is common in day-to-day living (anger, excitement, running). Taking sedatives (alcohol) or even normal sleep can be associated with a PCO₂ of ~ 50 mmHg.

2. RespirAct™

The inhaled gases used in this study are supplied by a computerized MPET system. During control conditions, room air will be supplied at flow greater than the subject's minute ventilation. The subject will be monitored continuously for heart rate, depth of sedation and saturation by pulse oximetry by an attending physician (neurosurgery/ICU or anesthesia). When there is any concern about the subject's condition an alarm button on the RespirAct™ will deliver 100% oxygen to the subject as an extra safety feature. The re-breathing circuit can be easily removed from the subject's face.

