The physiological effect jugular venous compressions used in this study are minimal and the brief period of jugular occlusion is similar to the effects produced

by straining, coughing and heavy lifting. Neck collar will apply only minimal pressure on the neck, which is comparable to wearing a tight dress shirt and a tie.

4. Ultrasound

There are no risks with the use of ultrasound. Orbital ultrasound is routinely done in all patients coming for cataract and retinal surgery at Toronto Western Hospital. Around 30 patients undergo transorbital ultrasound every day at UHN. Ultrasound Gel can be cold on contact with skin.

Data collection

Data collected will include:

- Volunteer demographics
- Medical history
- Vital signs- Heart rate, non-invasive blood pressure and cardiac output, oxygen saturation, end-tidal Co₂ levels.
- Optic nerve sheath diameter at normocapnia, 2 levels of hypercapnia and hypocapnia.
- Internal jugular vein diameter and flow in supine and Siting position with and without the neck collar.
- The minimal pressure needed to occlude the IJV.

Data Analysis

A paired t test will be used to compare the following changes in ONSD

- Normocapnia (baseline Pco₂) to hypercapnia (baseline+10 mmHg)
- Normocapnia (baseline Pco₂) to Hypercapnia (baseline+15mmHg)
- Normocapnia (baseline Pco₂) to hypocapnia (baseline -10mmHg)
- Neck collar ON and OFF at each Co₂ levels.

Sample size

Since this is a preliminary study to evaluate the effect of hypercapnia and hypocapnia and IJ compression on ONSD, only a small sample is required. We intend to enroll 15 subjects in this initial phase. Given the fact that the CO₂ manipulation technique using the RespirAct™ is a new method developed at the University of Toronto and not yet widely available, the lack of information in the literature regarding its utilization for this purpose is obvious. We believe that this small sample will be sufficient to demonstrate the feasibility of the test and set the stage for larger studies.

Project Feasibility

We anticipate no difficulty in obtaining 15 volunteers to participate in this study. The RespirAct™ gas blender used for CO₂ manipulation has been installed at 10 sites including John's Hopkins, University of Colorado, Duke University, University of Nottingham, University of Montreal, University of Texas, and McGill University. The device has a proven track record with regard to clinical implementation.

Figures

[figure not shown]

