Figure 1: Experimental protocol demonstrating target PetCO₂ levels with measurements being performed both while the venous compression collar is off and then subsequently applied.

[figure not shown]

Figure 2: An experiment of end-tidal CO₂ (PetCO₂) manipulation using MPET (RespirAct™). Please note the stable O₂ levels and the precision control of PetCO₂ levels.

[figure not shown]

Figure 3: Two-dimensional ocular sonography. A diagram showing the ultrasound probe, the ocular globe and the optic nerve with the optic nerve sheath diameter (ONSD) which was measured 3 mm behind the papilla using an electronic caliper (A X LONG measure) and an axis perpendicular to the optic nerve (B + LONG measure).

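### At +10, +15 and -10 mmHg the collar-on scans always follow the collar-off scans, so the ON/OFF test there estimates the collar effect plus any continuing ONSD response to the CO2 step.

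*Combined protocol and SAP*

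**What the plan says.** Under Carbon dioxide Manipulation, PetCO2 is raised 10 mmHg above baseline and kept there for 5 minutes while ONSD is scanned. Then "The venous compression neck collar will then be applied and ONSD measurements will be repeated", and CO2 goes back to baseline. The same sequence is used at +15 mmHg. The -10 mmHg step is described without mention of the collar and without a hold time.

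The collar section applies the collar at all four CO2 levels, hypocapnia included, and says "ONSD measurements will be measures before and after the collar". The Figure 1 caption agrees: scans are made "while the venous compression collar is off and then subsequently applied". No alternated order, no-collar time control, or repeat collar-off set at the same level is described.

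Data Analysis lists "Neck collar ON and OFF at each" CO2 level among the paired t tests. The background states that "we don't know how soon the ONSD changes with acute changes in intracranial pressure". Under Ultrasound measurement of ONSD, "Each eye will be examined 3 times by each investigator and the mean value of the ONSD will be used for further calculations". The Data collection list has "Optic nerve sheath diameter at normocapnia, 2 levels of hypercapnia and hypocapnia" but no scan times.

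Before the first CO2 step the text describes only this: "We will record baseline values for 120 seconds". It does not say when the normocapnia collar pair is taken.

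**The concern.** In every subject, at +10, +15 and -10 mmHg, the collar-on set is also the later set after the CO2 change. If ONSD is still moving in response to CO2 when the collar goes on, the rest of that movement is counted as collar effect. Suppose that ONSD rises with CO2 and with jugular occlusion. The collar effect is then exaggerated under hypercapnia and partly cancelled under hypocapnia.

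The gas system's speed does not settle this. The background's three-breath figure describes how fast PetCO2 reaches target, not how fast ONSD follows. Jugular occlusion is part of the hypothesis and the main objective, and three of the four planned collar contrasts are affected.

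**Working it through.** **No figure in the plan to reproduce.** The sample size of 15 is given without effect size, SD, alpha or power. Two-sided alpha of 0.05 is assumed below.

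**Is the effect separable?** Within one CO2 level, take a model with an intercept, a collar term and a time-position term. With OFF always first the design matrix has rank 2 of 3, so collar and time position cannot be told apart. The paired mean difference estimates collar effect plus drift.

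**Timing.** One set is 2 investigators x 2 eyes x 3 repeats = 12 scans, or 300/12 = 25 seconds per scan over the 5-minute hold. A second set then runs from about minute 5 to minute 10. This fits the 10-minute intervals given under Risks for raised CO2. Timing at -10 mmHg is assumed to be the same.

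**Bias with no collar effect.** Assume that ONSD approaches its new level exponentially with time constant T, which the documents do not give. The mean response over minutes a to b, as a share of the full CO2 effect, is 1 - T/(b-a) x (exp(-a/T) - exp(-b/T)). Two timings were tried: even (minutes 0-5 and 5-10) and late (minutes 3-5 and 8-10).

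| T (min) | Even: OFF, ON | Bias | Late: OFF, ON | Bias |
|---|---|---|---|---|
| 0.1 | 0.980, 1.000 | 0.020 | 1.000, 1.000 | 0.000 |
| 0.5 | 0.900, 1.000 | 0.100 | 0.999, 1.000 | 0.001 |
| 2 | 0.633, 0.970 | 0.337 | 0.859, 0.988 | 0.129 |
| 5 | 0.368, 0.767 | 0.400 | 0.548, 0.834 | 0.286 |
| 20 | 0.115, 0.311 | 0.196 | 0.181, 0.362 | 0.181 |

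**Chance of falsely declaring a collar effect.** This uses the noncentral t with 14 df and ncp = sqrt(15) x bias x CO2 effect, the CO2 effect being in SDs of the ON-OFF difference (assumed 1 or 2).

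| T (min) | Even, 1 SD | Even, 2 SD | Late, 1 SD | Late, 2 SD |
|---|---|---|---|---|
| 0.1 | 5.1% | 5.2% | 5.0% | 5.0% |
| 0.5 | 6.5% | 11.2% | 5.0% | 5.0% |
| 2 | 22.9% | 68.0% | 7.5% | 15.5% |
| 5 | 30.3% | 82.1% | 17.8% | 54.1% |
| 20 | 10.9% | 29.3% | 10.0% | 25.8% |

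**Masking at -10 mmHg.** Take a true, immediate collar effect of +1 SD and a CO2 effect of -1 SD. The observed difference becomes 1 - bias. Power falls from 95% to 67% (T = 2) and 58% (T = 5) with even timing, or to 88% and 73% with late timing.

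**Could drift within the collar-off repeats correct for this?** Assume independent scan error s only. The SD of the ON-OFF difference is s x sqrt(2/12) = 0.408s. Round 3 minus round 1, with 4 scans per round, has SD s x sqrt(2/4) = 0.707s, which is 1.73 times as large. The 95% CI half-width for n = 15 is 2.145/sqrt(15) = 0.554 SD. Scaling the drift to the 5 minutes between sets gives these half-widths, in SDs of the ON-OFF difference:
- rounds spread over 5 minutes (3.33 minutes between rounds 1 and 3): 0.554 x 1.73 x 5/3.33 = 1.4;
- rounds within minutes 3-5 (1.33 minutes): 0.554 x 1.73 x 5/1.33 = 3.6;
- back-to-back repeats of one eye (50 seconds): 0.554 x 1.73 x 300/50 = 5.8.

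The drift estimate is too imprecise to correct the contrast or to clear it.

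**Collar carry-over if the normocapnia pair comes first.** If the collar effect fades with the same T, the share left in the +10 collar-off set after a gap of g minutes is (1 - exp(-5/T)) x exp(-g/T) x mean of exp(-t/T) over 0-5. With only the 120-second baseline (g = 2) this is 0.918 x 0.368 x 0.367 = 12% (T = 2), or 0.632 x 0.670 x 0.632 = 27% (T = 5). With 5 more minutes (g = 7) it is 1% or 10%.

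**The case against.** The strongest reply is that the size is assumed throughout. The documents give no time constant, ONSD effect or SD, and the results run from nothing to 82% false positives. The top figure needs T near 5 minutes, a 2 SD effect and scanning from minute 0. That stands: the confounding is shown, a material bias is not. The study is also described as preliminary, with 15 subjects. That lowers the stakes, but these tests are still planned and are meant to inform larger studies.

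Three stronger readings are tempting, and the documents support none of them.
- A reader might infer that scan times will go unrecorded and the three repeats be discarded. The Data collection list is introduced as what the data will include. It does not spell out the collar-on ONSD values either, which the plan plainly needs, so it is not exhaustive. Using the mean in calculations does not mean that the repeats are lost.
- A reader might infer that the normocapnia pair is misplaced. Two sets of 12 scans in 120 seconds would need 5 seconds per scan, so the text leaves its position open. Figure 1 is not shown and may settle it.
- A reader might treat the normocapnia pair as a clean collar result. No CO2 step precedes it if it comes first, so it is less exposed, but it is still off-then-on.

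Alternating the collar order is the textbook answer. With no carry-over, an 8/7 split and a period-adjusted test hold the false-positive rate at about 5% with almost the same standard error (ratio 1.002). But if the collar effect fades with the same T, the collar-first order captures only 0.633 - 0.337 = 0.296 of it at T = 2, and 0.368 - 0.400 = -0.032 at T = 5. Averaged over the two orders, capture falls from 63% to 46% and from 37% to 17%. Keeping the fixed order is a judgement that this loss is worse than a plainly labelled contrast.

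**Conclusion.** The point holds as a limit on interpretation. The order is explicit at +10 and +15 mmHg; at -10 mmHg it rests on the collar section and the Figure 1 caption. At those levels the planned test cannot attribute an ON-OFF difference to the collar alone. The bias is about 13% to 40% of the CO2 effect if the time constant is 2 to 5 minutes, and negligible if ONSD settles within seconds. The range rests on an assumed exponential response, assumed scan windows and, at -10 mmHg, assumed timing. A reader might infer that the collar results will be wrong. The documents do not support that, because they do not say how fast ONSD responds.

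**What to change.** Keep the off-then-on order, and:

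1. Record the time of each ONSD scan from the CO2 change and the time the collar goes on. Keep the three repeat values as well as their mean. Take the repeats in rounds across eyes and investigators, not back to back.
2. Report the ON-OFF contrasts at +10, +15 and -10 mmHg as collar plus added time at that CO2 level, and do not attribute them to the collar alone.
3. Unless Figure 1 already shows it, take the normocapnia off/on pair before the first CO2 step, then allow a collar-off pause of about 5 minutes before the +10 step. Use this pair as the main collar contrast. Without the pause, the move could bias both the +10 collar contrast and the normocapnia-to-+10 comparison.
4. Show the drift within the collar-off repeats with its 95% CI as description only. At n = 15 it cannot lift the restriction in item 2.

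The cost is time stamps, a pause of about 5 minutes per subject and a more cautious conclusion for three contrasts. No scans are added, since the normocapnia pair is already planned.

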drainage. Among the methods available for CO₂ manipulation, we have shown that Model-based Prospective End-Tidal Targeting (MPET) system (RespirAct™-Thornhill research Inc) is the most reliable method for accurate and precise targeting of CO₂.⁹⁻¹⁰ Briefly, the RespirAct™ is a custom designed breathing circuit that uses computer controlled gas blending to quickly and precisely control end-tidal carbon dioxide levels⁹. The RespirAct™ has two main features for this study. First, it is capable of rapidly and precisely targeting a series of PetCO₂ independent of the subject's breathing pattern¹⁰. These changes can be induced within three breaths, are accurate to within ± 1 mmHg, and can be sustained at constant levels. Second, it has been shown in humans and animals that a unique characteristic of this system is that the end tidal CO₂ (PetCO₂) is precisely equal to arterial CO₂ (PaCO₂).⁹ With regards to venous outflow obstruction, both Valsalva maneuver (forced inspiration with closed glottis) and /or compression of internal jugular veins (IJV) are the two commonly used physiological methods that can cause an increase in ICP. However, compared to Valsalva maneuver which is dependent on the individual's effort and a variable effect, jugular venous compression is more reliable and reproducible method to increase ICP. Bilateral jugular occlusion is sometimes used during neurosurgical procedures during craniotomy opening especially in patients who are at risk of air embolism.⁽¹¹⁾ Jugular venous occlusion can be done using a custom made neck collar and previous investigations have used a similar device in a rat model to demonstrate the protective effects on slosh-mediated brain injury by increasing intracranial blood volume^{12,13}. While the collars have not yet been studied on people for their effectiveness at preventing

concussions, many studies have looked at the effect of neck collars on both jugular compression and ICP.^{14,15}

Aim of our study to determine the changes in ONSD with acute controlled changes in ICP in healthy volunteers. Transorbital ultrasound will be used for measuring the changes in ONSD. The controlled changes in ICP will be produced by manipulating the PCO₂ with the use of Respiract and jugular venous compression with the use of custom made neck collar.

References

References

1. Lundberg N. Continuous recording and control of ventricular fluid pressure in neurosurgical practice. *Acta Psychiatr Scand Suppl* 1960;36(149):1-193.

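### One fixed CO₂ order, with no ONSD set stated in the text at the returns to baseline, leaves the +15 and −10 mmHg contrasts confounded with elapsed time and carry-over

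*Combined protocol and SAP*

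**What the plan says.** The order is set out under Carbon dioxide Manipulation. It opens: "We will record baseline values for 120 seconds and then the PetCO₂ will be increased to +10 mmHg (Hypercapnia I) from baseline". That level is held for 5 minutes for the ONSD measurements. Then: "The venous compression neck collar will then be applied and ONSD measurements will be repeated". PetCO₂ goes back to baseline, with a reference to Figure 1. Next: "This sequence will again be repeated increasing the PetCO₂ to +15 mmHg (Hypercapnia II) from baseline before returning to baseline". Then: "The subject will then have PetCO₂ decreased to -10 mmHg (Hypocapnia) from baseline before returning to normal capnia", and the study stops.

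The section on the neck collar adds that the collar is also used at normocapnia and hypocapnia, with ONSD measured before and after. It does not say when in the session the normocapnia pair is taken.

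Data collection lists one normocapnia condition, two hypercapnia levels and hypocapnia. Data Analysis compares normocapnia with each of the three levels by paired t test. No order, period or time term is mentioned.

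Two statements in the background bear on the returns. On the device's control of end-tidal CO₂: "These changes can be induced within three breaths, are accurate to within ± 1 mmHg, and can be sustained at constant levels". On the outcome: "In addition, we don't know how soon the ONSD changes with acute changes in intracranial pressure".

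**The concern.** The return to baseline is defined by PetCO₂ alone. The device can reset PetCO₂ in a few breaths, but the protocol itself says that the timing of the ONSD response is unknown. The text asks for no measurement that would show whether the sheath has recovered before the next level starts.

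In all 15 subjects, level, position in the session and preceding exposure therefore coincide. The +15 level always follows +10 with the collar; the −10 level always follows +15 with the collar. A paired comparison removes differences between subjects, but not drift or carry-over within a session. Any residual distension would be read as part of the CO₂ effect at +15, and would offset a fall at −10. The planned data could not reveal either, although the aim is to learn how ONSD changes with controlled manipulation of CO₂.

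**Working it through.** The documents give no ONSD response time, return duration or drift, so there is no plan figure to reproduce. Three checks follow. All model inputs beyond the order of levels and the 5 minutes per set are assumptions.

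**1. Can the planned data separate level from time?** Take an intercept, three level effects and a linear time trend: 5 parameters.
- Opening baseline, +10, +15, −10: 4 distinct conditions, rank 4 of 5. Not separable.
- The same order with an ONSD set at every return, including the last: 7 positions, rank 5 of 5. Separable from a linear trend.

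**2. How large could carry-over be?** Assume a first-order ONSD response with time constant τ; plateaus of +1.0, +1.5 and −1.0 units at +10, +15 and −10; a collar effect of +0.5; 5-minute sets; and a normocapnia collar set run just before +10. For a set with target T that starts at y₀:
- mean reading = T + (y₀ − T)·(τ/5)·(1 − e^(−5/τ))
- end value = T + (y₀ − T)·e^(−5/τ)
- a return of r minutes multiplies the value by e^(−r/τ)

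Example with τ = 5 and r = 2:
- Normocapnia collar set ends at 0.5 × 0.632 = 0.316.
- +10 collar off ends at 1 − 0.684 × 0.368 = 0.748; collar on ends at 1.5 − 0.752 × 0.368 = 1.223.
- The return leaves 1.223 × 0.670 = 0.820.
- +15 reads 1.5 − 0.680 × 0.632 = 1.07. From a reset start it would read 1.5 × 0.368 = 0.55.
- +15 collar off ends at 1.250; collar on ends at 1.724; the return leaves 1.724 × 0.670 = 1.156.
- −10 reads −1 + 2.156 × 0.632 = +0.36. From a reset start it would read −0.37.

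Each cell below is the modelled reading v the reading from a reset start. The step is the difference between the two preceding columns.

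| Return (min) | τ (min) | −10 | +10 | +15 | Step +10 to +15 |
|---|---|---|---|---|---|
| 2 | 1 | −0.75 v −0.80 | 0.90 v 0.80 | 1.24 v 1.20 | 0.34 v 0.40 |
| 2 | 2 | −0.37 v −0.63 | 0.80 v 0.63 | 1.15 v 0.95 | 0.35 v 0.32 |
| 2 | 5 | +0.36 v −0.37 | 0.57 v 0.37 | 1.07 v 0.55 | 0.50 v 0.18 |
| 5 | 2 | −0.57 v −0.63 | 0.80 v 0.63 | 0.99 v 0.95 | 0.19 v 0.32 |
| 5 | 5 | +0.02 v −0.37 | 0.57 v 0.37 | 0.84 v 0.55 | 0.27 v 0.18 |

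Without the normocapnia collar set before +10, the later readings barely change (1.05 and +0.36 in the third row). The +10 reading then starts from reset.

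**3. How exposed are the t tests to drift?** Time from the midpoint of the 2-minute baseline to the midpoint of each collar-off set, with r = 2 or 5:
- +10: (2 + 5 + 2.5) − 1 = 8.5 min
- +15: (2 + 5 + 10 + r + 2.5) − 1 = 20.5 or 23.5 min
- −10: (2 + 5 + 10 + r + 10 + r + 2.5) − 1 = 32.5 or 38.5 min

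Assume two-sided α = 0.05, n = 15, and a noncentral t with 14 df and noncentrality δ√15, where δ is the drift in SDs of the paired difference. With no CO₂ effect and 0.1 SD of drift per block (δ = 0.1, 0.2, 0.3), the +10, +15 and −10 tests reject 6.5%, 11.2% and 19.2% of the time.

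**The case against.** **The returns are a washout, and Figure 1 may show measurements there.** This stands in part. Figure 1 is not shown, and its caption calls it the experimental protocol. Repeating the sequence could also be read as repeating the 120-second baseline recording. A reader might infer that nothing is measured at the returns; the documents support only that the text specifies no ONSD set there. Even if return sets exist, Data Analysis gives them no role.

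**Carry-over does not affect every contrast.** Correct. The +10 level follows no CO₂ step. It can carry over only from a normocapnia collar set, if that set is taken first.

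**Carry-over does not necessarily exaggerate the dose response.** Also correct. A reader might infer that the step from +10 to +15 is inflated. In the table it shrinks in two of five cases, because a preceding normocapnia collar set also raises the +10 reading. The +15 reading is raised only relative to a reset start; in every case it stays below the assumed plateau of 1.5.

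**Return sets would make a poor comparator.** This stands. They follow a collar-on block. If each set fills a 5-minute return and the before/after mean is subtracted, +15 reads 0.99 − (0.53 + 0.72)/2 = 0.37 at τ = 2 (reset start 0.95), and 0.84 − (0.77 + 1.06)/2 = −0.08 at τ = 5 (reset start 0.55).

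**This is a 15-subject preliminary study, and hypocapnia lies outside the stated hypothesis.** Both limit the consequence. Neither removes the confounding at +15, which is within the hypothesis.

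**Conclusion.** The concern holds for the +15 and −10 contrasts. As written, a CO₂ effect there cannot be told apart from elapsed time or from carry-over of the preceding CO₂-plus-collar block. The +10 contrast is exposed mainly to elapsed time, and least of the three.

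Relative to a reset start, carry-over would raise the +15 reading and hide or reverse a fall at −10. Its size is unknown: small if the ONSD time constant is about 1 minute, large if about 5. Both are assumed values, as are the return durations, plateaus, collar effect and drift. The sign change at −10 shows what the design could not detect; it is not a prediction.

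The finding rests on the text alone and would be eased, though not settled, if Figure 1 marks ONSD sets at the returns. It is worth correcting before the study starts, because the missing information is cheap to collect.

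**What to change.** 1. **Measure.** Take a collar-off ONSD set, with the same scans and operators, at the end of each return to baseline PetCO₂, just before the next level, and again after the last level. State when the normocapnia collar pair is taken. If Figure 1 already shows return sets, say so in the text.
2. **Analyse.** Keep the opening baseline as the main comparator. Report each return set minus the opening baseline with a 95% confidence interval as the carry-over and drift check. With n = 15 its half-width is 2.145/√15 = 0.55 SD of the paired difference, so an interval that covers zero does not prove recovery. Use the adjacent-baseline comparison only as a sensitivity analysis for slow drift.
3. **State the consequence.** If ONSD has not returned to its opening value, report that the +15 and −10 contrasts cannot be attributed to CO₂ alone.
4. **Order.** Whether the order of levels can be varied is for the investigators to decide. If it is varied, use sequences balanced for the preceding level (all six orders) and include period in the analysis. Rotating the present order in one cyclic 3×3 square would leave +15 preceded only by +10, and −10 only by +15. Fifteen subjects do not divide evenly over six orders (15/6 = 2.5). Varying the order separates the levels from one another, but the opening baseline is still always first, so item 1 is needed either way.

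Cost: up to 3 extra sets × 5 min = about 15 min more supine time per subject at normal PetCO₂, and a few lines of analysis text. No extra subjects or equipment.
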